### 5.3. Medical History

General medical history data will be collected at screening and listed only. General medical history data will be coded using the current version of Medical Dictionary for Regulatory Activities (MedDRA).

## **6. EFFICACY ANALYSES**

As this study is still in phase I of the drug development, p-values from statistical comparisons will not be adjusted for multiplicity, so the results should be interpreted with caution.

### **6.1. Primary Efficacy Analysis**

#### **6.1.1. Definition of Primary Efficacy Endpoint**

The primary efficacy endpoint is the maximum change from baseline in plasma  $\log_{10}$  HIV-1 RNA at any postdose timepoint up to Day 81 for Cohorts 1-3 or Day 134 for Cohorts 4-6.

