 - If ARV regimen is changed ≥ 45 days prior to Pre-Baseline/Day -13, plasma HIV-1 RNA < 50 copies/mL at Pre-baseline/Day -13 visit is required.
- No documented history of resistance to any components of the current ARV regimen
- Availability of a fully active alternative ARV regimen, in the opinion of the Investigator, in the event of discontinuation of the current ARV regimen with development of resistance.
- Hgb ≥ 11.5 g/dL (males) or ≥ 11 g/dL (females)
- WBC ≥ 4000 cells/ μ L
- Platelets $\geq 150,000$ /mL
- ANC ≥ 1500 cells/ μ L
- CD4 count ≥ 400 cells/ μ L
- Albumin ≥ 3.9 g/dL
- ALT and AST $\leq 2 \times$ ULN
- Estimated glomerular filtration rate ≥ 60 mL/min
- No autoimmune disease (e.g. lupus erythematosus, rheumatoid arthritis, inflammatory bowel disease, sarcoidosis, moderate or severe psoriasis)
- No evidence of current HBV infection
 - Positive anti-HBs antibody and negative HBsAg results are acceptable

- No evidence of current HCV infection
 - Positive anti-HCV antibody and negative HCV PCR results are acceptable
- No documented history of pre-ART CD4 nadir < 200 cells/μL
 - Unknown pre-ART CD4 nadir is acceptable
- No history of Class C AIDS-Defining Condition
 - No acute febrile illness within 35 days prior to Pre-Baseline/Day -13

Study Visits and
Procedures:

Visit Schedule:

The main study phase consists of a screening period of up to 35 days, a pre-treatment period of 14 Days (from Day -13 to Day 1), treatment period of 71 days (Cohorts 1 to 3), 127 days (Cohorts 4 to 6), CCI and a follow-up period of 30 days after the last dose of study drug is taken. Enrolled subjects will undergo the following scheduled study visits:

Cohort 1 to Cohort 3

Day -13 (**Pre-Baseline**)

Day 1 (**Baseline/Dose 1**), Day 3, Day 5, Day 8, Day 11

Day 15 (**Dose 2**), Day 17, Day 19, Day 22, Day 25

Day 29 (**Dose 3**), Day 31, Day 33, Day 36, Day 39

Day 43 (**Dose 4**), Day 45, Day 47, Day 50, Day 53

Day 57 (**Dose 5**), Day 59, Day 61, Day 64, Day 67

Day 71 (**Dose 6**), Day 73, Day 75, Day 78, Day 81

Day 101 (**End of Study**)

Cohort 4

Day -13 (**Pre-Baseline**)

Day 1 (**Baseline/Dose 1**), Day 2, Day 3, Day 8

Day 15 (**Dose 2**), Day 22

Day 29 (**Dose 3**), Day 36

Day 43 (**Dose 4**), Day 50

Day 57 (**Dose 5**), Day 58, Day 59, Day 64

Day 71 (**Dose 6**), Day 78

Day 85 (**Dose 7**), Day 92

Day 99 (**Dose 8**), Day 106
Day 113 (**Dose 9**), Day 120
Day 127 (**Dose 10**), Day 128, Day 129, Day 134
Day 157 (**End of Study**)

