Whole blood ISG mRNA panel: **For Cohorts 1 to 3**, immediately before and 2 days and 7 days after each dose of study drug, and at the end of the study (Day 101). **For Cohorts 4 to 9**, immediately before and 1 day, 2 days and 7 days after doses 1, 4 (only if Cohort 6 subjects receive 12 mg starting at Dose 4), 5 and 10. CCI

TLR7 genotyping: at Pre-Baseline/Day -13

Virology:

Plasma HIV-1 RNA: at every visit except Pre-Baseline (Day -13).

Cell-associated HIV-1 RNA/DNA (CAVR/CAVD), and plasma HIV-1 RNA by Single Copy Assay (SCA) will be collected immediately before and two days post Doses 1, 4, 6 and at end of the study (Cohort 1 to 3); immediately before and two days post Doses 1, 5, 10 and at end of the study (Cohorts 4 to 9). CCI

HIV-1 reservoir measurements: at Pre-Baseline/Day -13 and at the end of the study (Cohorts 4 to 9). CCI

Immunology:

Peripheral blood immune cell numbers for T/B/NK/pDC/mDC including: CD4 and CD8 populations, CD4/CD8 ratio, CD4% and lymphocyte activation (T, B and NK cells) by flow cytometry will be collected immediately before and two days post Doses 1, 3, and 6 (Cohorts 1 to 3), and immediately before, one and two days post Doses 1, 5 and 10 (Cohorts 4 to 9). CCI

FoxP3+ Treg cells by flow cytometry will be collected immediately before Doses 1, 3, and 6 (Cohorts 1 to 3), and immediately before Doses 1, 5 and 10 (Cohort 4 to 9). CCI

Changes in the levels of antiviral cytokines and inflammatory markers by chemiluminescence: immediately before and 2 days and 7 days after each dose, and at the end of the study (Cohorts 1 to 3). For subjects in Cohorts 4 to 9, immediately before, post dose days 1, 2 and 7 after Doses 1, 4 (only if Cohort 6 subjects receive 12 mg at Dose 4), 5 and 10. CCI

PBMC Intracellular cytokine staining (ICS) for Treg cells: immediately before and 2 days after Doses 1 and 6 for subjects in Cohorts 1 to 3.

HIV-specific T-cell responses by ELISPOT will be collected at Pre-Baseline/Day -13, immediately before Dose 6 and at the end of study for subjects in **Cohorts 1 to 3**.

For subjects in Cohorts 4 to 9, HIV-specific polyfunctional T cell Intracellular Cytokine Staining (ICS) and HIV-specific T-cell responses by ELISPOT will be collected at Pre-Baseline/Day -13 and at the end of the study. **CCI**

Stool sample will be obtained for microbiome analysis. (Day 1 and Day 157 for **Cohorts 5 to 9**). **CCI**

CCI

Additional End of Study Procedures:

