GS-9620 is an orally-administered toll-like receptor (TLR) 7 agonist currently in clinical development for the treatment of HIV. In vitro, GS-9620 appears to mediate both HIV-1 “kick” and “kill” activity. In a rhesus macaque model of chronic SIV infection, treatment with GS-9620 or its close analog GS-436986 has also demonstrated the ability to both “kick” and “kill”: treatment resulted in transient detection of plasma viremia within 24-72 hours of dosing, decreases in ex vivo SIV production from T-cell receptor stimulated PBMC cultures or immune cell isolates of peripheral lymph nodes comparing pre-treatment to post-dosing samples and a $\sim 0.5 \log_{10}$ lower viral load set-point after discontinuation of ART {Lim 2018}. Most importantly, in a subset of animals, there was a lack of detectable plasma virus (< 50 SIV RNA copies/mL) for > 2 years after discontinuation of ART. During the off ART phase, two animals from one of the studies had no viral rebound after administration of antibodies depleting NK and CD8+ lymphocytes or transfer of viral infection after infusion of mononuclear immune cells from lymph node and peripheral blood into naïve animals; implying a substantial reduction in viral reservoir. The administration of multiple doses of GS-9620 has been shown to be safe in clinical studies of healthy subjects (single doses up to 12 mg), and hepatitis B virus (HBV)-infected subjects (multiple doses up to 4 mg). This study will therefore investigate the safety and efficacy of GS-9620 in HIV-infected individuals who are virologically suppressed on ART.

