### **3.2. Subject Grouping**

For analyses based on the All Randomized Analysis Set or the FAS, subjects will be grouped by randomized treatment. For other analyses, subjects will be grouped by actual treatment received. The actual treatment received will differ from the randomized treatment only when the actual treatment received differs from randomized treatment for the entire treatment duration.

Subjects who received placebo in different cohorts will be combined as one placebo group for analysis purposes if applicable. The treatment groups for analysis are defined as follows:

- Treatment 1: VES 1 mg (in Cohort 1)
- Treatment 2: VES 2 mg (in Cohort 2)
- Treatment 3: VES 4 mg (in Cohort 3)
- Treatment 4: VES 6 mg (in Cohort 4)
- Treatment 5: VES 8 mg (in Cohort 5)
- Treatment 6: VES 10/12 mg (in Cohort 6)
- Treatment 7: Placebo (in all Cohorts)

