### **6.2. Secondary Efficacy Analyses**

#### **6.2.1. Definition of Secondary Efficacy Endpoints**

Secondary efficacy endpoints include the following:

- Change from baseline in plasma  $\log_{10}$  HIV-1 RNA at postbaseline visits
- Proportion of subjects with plasma HIV-1 RNA  $\geq 50$  copies/mL at any postdose timepoint (up to 10 days after each dose for Cohorts 1-3 and 7 days after each dose for Cohorts 4-6)

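### The maximum HIV-1 RNA change and the any-value-at-or-above-50 endpoint are not like for like across cohorts: at 6 mg the 24-72 hour period is sampled after only 3 of 10 doses

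*SAP*

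**What the plan says.** **Endpoints.** SAP 6.1.1 takes each subject's maximum change from baseline in log10 "HIV-1 RNA at any postdose timepoint up to Day 81 for Cohorts 1-3 or Day 134 for Cohorts 4-6". SAP 6.2.1 counts subjects with any value of at least 50 copies/mL, "up to 10 days after each dose for Cohorts 1-3 and 7 days after each dose for Cohorts 4-6".

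**Comparisons.** SAP 6.1.3 and 6.2.2 compare each active group with pooled placebo, by Wilcoxon rank sum and Fisher's exact test respectively, at two-sided 0.05. SAP 3.2 says: "Subjects who received placebo in different cohorts will be combined as one placebo group for analysis purposes if applicable". SAP 6.1.2 calls the primary comparison exploratory.

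**Sampling.** Under Virology, the Protocol Synopsis has HIV-1 RNA drawn at all visits other than Day -13, so the visit list is the sampling list. In Cohorts 1-3 the pattern after each dose is that of Dose 1: "Day 1 (Baseline/Dose 1), Day 3, Day 5, Day 8, Day 11". In Cohort 4, Doses 1, 5 and 10 have early visits, for example "Day 57 (Dose 5), Day 58, Day 59, Day 64". The other seven doses do not, for example "Day 71 (Dose 6), Day 78". Protocol 6.4.5 adds visits two days after Doses 3, 4, 6, 7, 8 and 9 for Cohorts 5 to 9 only.

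**Timing of viremia.** Protocol 1.1 reports of the macaque studies that "treatment resulted in transient detection of plasma viremia within 24-72 hours of dosing". Sections 1.2.2 and 1.3 repeat this.

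**The concern.** A maximum, or a count of subjects who ever cross a threshold, rises with the number of samples and with how well they cover the period when the signal is present. Here both differ by cohort, and cohort is the same thing as dose. Cohort 4 lies between cohorts that were sampled early after all or nearly all doses. A short-lived effect of the same size at 4, 6 and 8 mg would tend to show a dip at 6 mg.

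The 6 mg group is also compared with a placebo group in which 10 of 12 subjects have more samples than any 6 mg subject. What is at stake is the reading of the dose trend for a primary objective, the virologic effect on plasma HIV-1 RNA.

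**Working it through.** The plan gives no sampling count or power figure to reproduce, so the counts below come from the visit lists.

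**1. Scheduled post-dose samples**

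| | Cohorts 1-3 | Cohort 4 | Cohorts 5-6 |
|---|---|---|---|
| Doses | 6 | 10 | 10 |
| Secondary endpoint | 6×4 = 24 | 3×3 + 7×1 = 16 | 16 + 6 = 22 |
| Later pre-dose samples | 5 | 9 | 9 |
| Primary endpoint | 29 | 25 | 31 |
| Doses with a sample at 24-72 h | 6 of 6 | 3 of 10 | 9 of 10 |
| Samples at 24-72 h | 6 | 6 | 12 |

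Cohort 4 misses Doses 2, 3, 4, 6, 7, 8 and 9. Cohorts 5-6 miss Dose 2.

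**2. Can anything close the gap?** The seven-day visit has a window of ±1 day (Protocol 6.4.3), so it falls on days 6-8 and cannot reach 72 hours. SAP 3.8.2 keeps unscheduled results out of the summary tables and lists no exception for HIV-1 RNA.

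**3. Chance of catching a short spike.** Let q be the chance per dose of a spike confined to 24-72 hours, and m the number of doses covered. The chance of seeing at least one is 1 − (1 − q)^m. The values of q are assumptions.

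| q | Cohorts 1-3 (m=6) | Cohort 4 (m=3) | Cohorts 5-6 (m=9) |
|---|---|---|---|
| 5% | 26% | 14% | 37% |
| 10% | 47% | 27% | 61% |
| 20% | 74% | 49% | 87% |

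Part of the difference between Cohorts 1-3 and 5-6 reflects 6 against 10 doses. Cohorts 4 and 5-6 have the same number of doses, so the gap between them is due to the schedule alone.

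**4. No drug effect, secondary endpoint.** Assume independent blips with probability r per sample, so that the chance of any is 1 − (1 − r)^n. Placebo is weighted 6:2:4 over the three schedules. At r = 2%, 6 mg gives 1 − 0.98^16 = 28%, and pooled placebo gives (6×38.4 + 2×27.6 + 4×35.9)/12 = 36%. At 1% the figures are 15% and 20%; at 3%, 39% and 49%. On the primary endpoint's counts (29, 25, 31), 2% gives 40% and 44%, a smaller gap.

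**5. The planned tests (6 active, 12 placebo).** The Wilcoxon test was simulated with assumed blip heights, exponential with mean 0.4 log10 above 19 copies/mL.
- No drug effect: Cohort 4 rejects in 2.6% (1% blips per sample) or 5.1% (5% blips) of runs.
- The same drug effect in every group (q = 20%, 1% blips): 60% in Cohorts 1-3, 26% in Cohort 4 and 81% in Cohorts 5-6.

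For Fisher's exact test with no drug effect, exact enumeration with the step 4 probabilities gives Cohort 4 rejection rates of 0.6%, 2.1%, 3.6% and 4.4% at blip rates of 1%, 2%, 3% and 5%.

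**6. Days shared by all six cohorts.** To Day 78 these are Days 3, 8, 15, 22, 29, 36, 43, 50, 57, 59, 64, 71 and 78. Only Days 3 and 59 lie 24-72 hours after a dose. Days 15, 29, 43, 57 and 71 are pre-dose samples 14 days after the previous dose, so they fall outside the SAP's secondary window, which leaves 8 days. With two doses covered, detection at q = 10% is 1 − 0.9² = 19% in every cohort. In the step 5 simulation (q = 20%), Wilcoxon rejection is about 32% in every cohort.

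**The case against.** Five objections have weight.

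- **The timing is from macaques.** The protocol gives 24-72 hours as rationale and does not state it as the expected human timing. Its dose-limiting toxicity rule allows 10 days for an increase to resolve, and viremia lasting to day 7 would be sampled after all 10 doses in Cohort 4. This stands: step 3 is a worst case for duration. The protocol does, however, place its single-copy and cell-associated RNA samples two days after selected doses, so the early period matters to its own design.
- **By-visit comparisons are already planned.** SAP 6.2.2 analyses change from baseline at each visit in the same way as the primary endpoint, so Days 3 and 59 are compared like for like. This stands, but it does not supply a matched maximum or a matched any-value endpoint.
- **Cohort 4 has six samples at 24-72 hours, as many as Cohorts 1-3.** True, but they fall after three doses, so a short spike after any of the other seven is missed.
- **The analysis is exploratory and unpowered.** True. The descriptive dose trend is affected with or without a test.
- **Restricting to common days loses information.** True, and decisive against replacing the planned analysis: at q = 10% detection would fall from 47%, 27% and 61% to 19% throughout.

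A reader might infer that the endpoint cannot be compared with placebo at all, or that only 6 mg is affected. The documents support neither. Rejection rates with no drug effect stay near or below 5%, and Cohorts 5-6 also lack an early sample after Dose 2.

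**Conclusion.** The point holds as a matter of comparability and sensitivity. The counts follow directly from the visit lists: early samples after 3 of 10 doses at 6 mg, against 6 of 6 and 9 of 10 elsewhere, and 16 secondary-endpoint samples against 24 and 22. The consequence depends on viremia being short. If spikes are confined to 24-72 hours at an assumed 10% per dose, 6 mg shows at least one in 27% of subjects, where the Cohort 5-6 schedule would show 61% over the same ten doses. If viremia usually lasts a week, the loss is much smaller.

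The harm is a possible spurious dip at 6 mg and reduced power there, not false-positive findings. Nothing in the SAP tells the reader to allow for it.

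**What to change.** Keep the planned full-schedule analyses and add the following.

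- **SAP 6.1.3:** a supplementary comparison of the maximum change, each dose against pooled placebo and descriptively across doses, using only Days 3, 8, 15, 22, 29, 36, 43, 50, 57, 59, 64, 71 and 78.
- **SAP 6.2.2:** the same for any value of at least 50 copies/mL, using only Days 3, 8, 22, 36, 50, 59, 64 and 78.
- **Interpretation:** state that a lower result at 6 mg is not to be read as lower activity unless the common-day analysis agrees, because its 24-72 hour period was sampled only after Doses 1, 5 and 10.

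The cost is SAP wording and one extra table per endpoint, with no new data. The common-day analysis is less sensitive because it has only Days 3 and 59 in the early period and does not use Doses 7-10. It therefore supplements the planned comparison. Matching placebo by schedule is less workable, since Cohort 4 has only 2 placebo subjects.

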#### **6.1.2. Statistical Hypotheses for Primary Efficacy Endpoint**

The analysis of maximum change from baseline in plasma  $\log_{10}$  HIV-1 RNA at any postdose timepoint up to Day 81 for Cohorts 1-3 or Day 134 for Cohorts 4-6 between a VES treatment group and pooled placebo group is exploratory in nature and no formal hypothesis testing was planned.

#### **6.1.3. Analysis of Primary Efficacy Endpoint**

The maximum change from baseline in plasma  $\log_{10}$  HIV-1 RNA at any postdose timepoint up to Day 81 for Cohorts 1-3 or Day 134 for Cohorts 4-6 will be calculated for all subjects in the full analysis set using available on-treatment HIV-1 RNA data up to Day 81 for Cohorts 1-3 or Day 134 for Cohorts 4-6, and summarized by treatment group using descriptive statistics (n, mean, SD, 95% CI, median, Q1, Q3, minimum, and maximum).

The primary efficacy endpoint will be compared between each active treatment group and the pooled placebo group using a Wilcoxon rank sum test at a two-sided 0.05 significant level.

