3. STUDY DESIGN

3.1. Endpoints

The primary safety endpoint of this study is:

- Incidence of treatment-emergent SAEs and all treatment-emergent adverse events

The primary virology endpoint of this study is:

- Maximum change from baseline in plasma HIV-1 RNA at any post-dose time point

The secondary endpoints of this study are:

- Change from baseline in plasma HIV-1 RNA at post-baseline visits
- Proportion of subjects with plasma HIV-1 RNA > 50 copies/mL at any post-dose timepoint

The exploratory endpoints of this study are:

- [REDACTED]
- [REDACTED]
- [REDACTED]

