to 6, CCI of their assigned study treatment administered once every other week. For all subjects in Cohort 6, Dose 4 (Day 43) will occur after SEC review has been completed. If dose escalation is approved by the SEC, subjects in Cohort 6 will receive 12 mg of VES or placebo from Doses 4 to 10; if dose escalation is not approved by the SEC, subjects will continue receiving 10 mg of VES or placebo from Doses 4 to 10.

For Cohorts 1 to 3, dosing visits will occur at Day 1, Day 15, Day 29, Day 43, Day 57, and Day 71. For Cohorts 4 to 9, dosing visits will occur at Day 1, Day 15, Day 29, Day 43, Day 57, Day 71, Day 85, Day 99, Day 113 and Day 127. CCI

For Cohorts 1 to 4, subjects will fast for at least 2 hours before dosing. For Cohorts 5 to 8, subjects will fast overnight (at least 8 hours) before dosing. CCI

The Investigator will verify the subject's continued eligibility for dosing at post-Baseline dosing visits, including the absence of DLTs and (for females of childbearing potential) a negative urine pregnancy test, prior to dosing. All doses will be directly administered by blinded site staff.

Laboratory analyses (hematology, serum chemistry, and urinalysis) will be performed weekly for Cohorts 1 to 3. For Cohorts 4 to 9, these labs will be collected on dosing days, seven days post dose (starting from Dose 4), at end of study, and early study drug discontinuation (ESDD). For Cohorts 6, CCI these labs will also be collected on Day 2 and two days post dose (starting from Dose 5). CCI

Urine pregnancy test (for females of childbearing potential) will be performed prior to each dose. Vital signs (blood pressure, pulse, respiration rate and temperature) will be measured at all dosing visits.

Plasma HIV-1 RNA will be measured at every visit except Pre-Baseline (Day -13). Cell-associated HIV-1 RNA/DNA (CAVR/CAVD), and plasma HIV-1 RNA by SCA will be collected immediately before and two days post Doses 1, 4, 6 and at end of the study (Cohort 1 to 3); immediately before and two days post Doses 1, 5, 10 and at end of the study (Cohorts 4 to 9). CCI

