##### **3.1.2. Full Analysis set**

The Full Analysis Set (FAS) will include all subjects who (1) were randomized into the study and (2) have received at least one dose of study drug. Subjects will be grouped according to the treatment to which they were randomized. For the FAS, all efficacy data, including data collected after the last dose of study drug, will be included, unless specified otherwise. This is the primary analysis set for efficacy analyses.

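### SAP 6.1.3 limits the primary HIV-1 RNA endpoint to on-treatment data, a term neither document defines, so the maximum for subjects who stop dosing early is not fixed

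*SAP*

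**What the plan says.** Protocol 3.1 defines the primary virology endpoint as "Maximum change from baseline in plasma HIV-1 RNA at any post-dose time point". Protocol 8.1.2 and 8.5.1 say the same on the log10 scale.

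SAP 6.1.1 adds an end day: the maximum is taken "at any postdose timepoint up to Day 81 for Cohorts 1-3 or Day 134 for Cohorts 4-6". SAP 6.1.2 repeats that scope.

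SAP 6.1.3 repeats it once more and then narrows the input: the maximum is calculated "using available on-treatment HIV-1 RNA data up to Day 81 for Cohorts 1-3 or Day 134 for Cohorts 4-6". The word on-treatment is not defined in either document.

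SAP 3.1.2 sets the general rule for the full analysis set: "all efficacy data, including data collected after the last dose of study drug, will be included, unless specified otherwise".

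Two other SAP conventions could be borrowed to interpret the word. SAP 6.2.1 counts values for the secondary endpoint "up to 10 days after each dose for Cohorts 1-3 and 7 days after each dose for Cohorts 4-6". SAP 3.1.3 and the safety sections use last dose plus 30 days.

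**The concern.** The definition and the analysis of the primary endpoint do not take the same data. For a subject dosed to schedule this need not matter. For a subject who stops early, the analysis section may discard samples that the definition section counts, and the SAP does not say how many.

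Early stopping is not independent of the endpoint. Under protocol 6.8.1 a raised HIV-1 RNA result causes the next dose to be withheld. A subject who then starts a new ART regimen receives no further study drug but may still be monitored. Under protocol 7.6.1 a post-dose rise that does not resolve within 10 days is a dose-limiting toxicity, for which dosing may be discontinued. Protocol 6.5.2 asks sites to try to keep early stoppers in follow-up. Values after the last dose can therefore exist inside the primary window, and they may belong to the subjects with the strongest virologic response. A filter tied to dosing could remove data partly because of the outcome, which would lower the maximum.

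**Working it through.** **1. The window end days.** The SAP gives the dosing days: "For Cohorts 1 to 3, dosing visits will occur at Day 1, Day 15, Day 29, Day 43, Day 57, and Day 71", and for later cohorts the schedule ends "Day 85, Day 99, Day 113 and Day 127". Adding the post-dose windows of SAP 6.2.1 to the last scheduled dose:

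- Cohorts 1-3: 71 + 10 = 81
- Cohorts 4-6: 127 + 7 = 134

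Both stated end days reproduce. The window thus runs past the final scheduled dose by design, so for completers the sentence implies that on-treatment extends at least to Day 81/134.

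**2. An early stopper.** Take a subject whose last dose is Dose 3 (Day 29) and who attends every later visit. The visit days come from the study procedures tables. The scheduled post-dose HIV-1 RNA samples in the primary window number 29 (Cohorts 1-3), 25 (Cohort 4) and 31 (Cohorts 5-6). Each cell shows samples kept in the 14 days after the last dose, then samples kept in the whole window.

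| Scope | Cohorts 1-3 | Cohort 4 | Cohorts 5-6 |
|---|---|---|---|
| Last dose + 10 days (Cohorts 1-3) or + 7 days (Cohorts 4-6) | 4 of 5; 14 of 29 | 1 of 2; 7 of 25 | 2 of 3; 8 of 31 |
| Last dose + 30 days (Day 59) | 5 of 5; 21 of 29 | 2 of 2; 12 of 25 | 3 of 3; 14 of 31 |
| No filter (SAP 6.1.1) | 5 of 5; 29 of 29 | 2 of 2; 25 of 25 | 3 of 3; 31 of 31 |

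In Cohorts 5-6 the three samples are on Days 31, 36 and 43. The shorter cut (Day 36) misses a rise first seen on Day 43. The 30-day cut keeps the whole dosing interval in which the last dose acted and loses only later data.

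**3. What one lost value could do (illustration; the viremia is assumed).** SAP 3.7 imputes results below 20 copies/mL as 19. A peak of 200 copies/mL from that floor is log10(200/19) = 1.02. If it is lost and the subject's maximum falls to zero change, a six-subject mean drops by 1.02/6 = 0.17 log10. For peaks of 50 and 1000 copies/mL the drops are 0.07 and 0.29.

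For the Wilcoxon comparison, each active group has 6 subjects and pooled placebo has 2 × 6 = 12. Suppose all responders are active and everyone else is tied at the floor. The exact two-sided p is then the chance that all responders fall in the active group:

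- three responders: C(6,3)/C(18,3) = 20/816 = 0.025
- two responders: C(6,2)/C(18,2) = 15/153 = 0.098

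SAP 6.1.3 does not say whether the test is exact. The normal approximation with continuity correction gives 0.012 and 0.049 for the same two cases, so the crossing of 0.05 is specific to the exact test.

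**The case against.** The strongest reply is that the word may do little or nothing. SAP 3.8.2 excludes from summaries only data after the follow-up visit or last dose plus 30 days, whichever is later, and the safety sections use a 30-day period. Read that way, on-treatment keeps the whole episode that led to stopping. This stands: the loss depends on the definition.

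The stopping route is also narrow. Withheld dosing may resume, and viremia between two doses is then kept if on-treatment runs from first to last dose. Discontinuation for a dose-limiting toxicity is discretionary. Subjects with primary resistance mutations leave the study. Retention of early stoppers is only to be attempted. Protocol 1.4 reports no dose-limiting toxicities in the 1 to 6 mg cohorts. SAP 6.1.2 calls the comparison exploratory, with no formal hypothesis testing. All of this limits the size of the problem. It does not supply the definition.

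A reader might go further on three points, and the documents do not support any of them:

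- **That on-treatment ends at the last dose date**, so that every completer loses the response to the final dose. The Day 81/134 limits in the same sentence would then have no effect for a subject dosed on schedule.
- **That SAP 6.1.3 contradicts SAP 3.1.2.** The latter allows exceptions, and 6.1.3 can be one.
- **That the protocol expressly counts data after the last dose.** It says any post-dose time point and goes no further.

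**Conclusion.** The concern holds as an undefined restriction on the primary endpoint. SAP 6.1.1 and 6.1.3 agree for completers on the natural reading, and can disagree for subjects who stop dosing early and stay in follow-up. In the Cohort 5-6 example the analysis uses 8 or 14 of 31 scheduled samples, against 31 under the definition.

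Bias toward a smaller maximum is possible, not certain. It requires three things: a subject who stops because of, or around, viremia; samples taken afterwards; and a definition that excludes the samples carrying the peak. With 6 subjects per dose group, one such subject is 1/6 = 17% of the group. The p-values in the illustration rest on an assumed pattern of responders and on the exact test, and they decide nothing that the plan prespecifies. The point is worth correcting because the remedy is cheap and the endpoint is primary.

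**What to change.** Delete the word on-treatment from SAP 6.1.3 so that it matches 6.1.1. Add one sentence stating that every HIV-1 RNA result after the first dose, up to the nominal Day 81 or Day 134 visit, counts toward the maximum. It should include results after early stopping and an early study drug discontinuation sample that falls in the window. Because SAP 3.8.2 keeps unscheduled visits out of summary tables and treats early termination as a separate visit, the sentence should say explicitly that it also covers unscheduled retests and that discontinuation sample.

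The cost is one sentence before the blind is broken. The downside is that some samples from early stoppers will have been taken long after dosing or on a changed ART regimen. Flag those values, or show a supportive summary without them.

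Defining the term in days after the last dose would also remove the ambiguity. It would leave 6.1.3 narrower than 6.1.1 for early stoppers, so 6.1.1 would then need the same limit. Deletion is simpler: if the filter was meant to do nothing, nothing is lost.
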